11. Seropositive for hepatitis C (except in the setting of a sustained virologic response [SVR], defined as aviremia at least 12 weeks after completion of antiviral therapy)
12. Chronic obstructive pulmonary disease (COPD) with a Forced Expiratory Volume in 1 second (FEV1) less than 50% of predicted normal
13. Moderate or severe persistent asthma within the past 2 years, or uncontrolled asthma of any classification. Note that participants who currently have controlled intermittent asthma or controlled mild persistent asthma are allowed to participate
14. History of prolonged QTc > 480ms or ventricular arrhythmia on screening EKG or history of ventricular arrhythmia QTc or ventricular arrhythmia
15. Myocardial infarction within 6 months before randomization, or unstable or uncontrolled disease/condition related to or affecting cardiac function (e.g., unstable angina, congestive heart failure, New York Heart Association Class III-IV)
16. Received any prior anti-myeloma therapy within 14 days of planned study treatment

Statistical Considerations:

Brief Statistical Rationale

The phase 1b will estimate the maximum tolerated dose (MTD) by a standard 3+3 design using data collected in the dose escalation phase. MTD will be defined for each dosing level. A maximum of 2 dose levels are planned (35.5 mg/m²/day to 45 mg/m²/day). For phase 1b the number of evaluable patients is planned to be 12.

The phase 2 portion will evaluate the clinical activity of Dara + Pom + Dex + ATRA. A Simon's two-stage minimax design will be used. The null hypothesis that the true response rate is $\leq 30\%$ will be tested against a one-sided alternative of 50% or higher at the one-sided type I error of 0.10 at 80% power. In the first stage, 12 patients will be accrued. If there are 4 or fewer responses in these 12 patients, the study will be stopped due to futility. Otherwise, 16 additional patients will be accrued for a total of 28. The null hypothesis will be rejected if 12 or more responses are observed in 28 patients.

Adverse events (AEs) will be summarized by treatment group and overall. Categorical variables such as ORR will be tabulated by treatment group and overall. Time to event variables will be analyzed using Kaplan-Meier survival curves and Kaplan-Meier medians will be provided.

Statistical Power Calculations

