This Simon's two-stage design yields a type I error rate of 0.095 and power of 0.802 when the true response rate is 48%. The probability of early stopping due to futility is approximately 49.2%.

Primary Analysis

After a maximally 42 patients are enrolled in the phase 1b and phase 2 portions combined, a primary interim efficacy analysis and the second safety analysis will be conducted. The subset safety analysis will be also descriptively performed based on the previous exposure groups (Dara + Len + Dex or Dara + Pom + Dex).

Overall response rate (ORR) and stringent complete response (sCR)/CR/near CR (nCR) according to IMWG criteria will be determined and corresponding 2-sided 80% exact binomial confidence interval will be calculated. The subset ORR analysis will be also performed based on the previous exposure groups (Dara + Len + Dex or Dara + Pom + Dex).

The Kaplan-Meier (KM) method will be used to estimate the time-to-event endpoints such as time on study (TOS), duration of response (DOR), time to progression (TTP), progression-free survival (PFS) and overall survival (OS) distributions. The subset time-to-endpoint outcome analysis will be also performed using the KM method based on the previous exposure groups (Dara + Len + Dex or Dara + Pom + Dex).

Adverse events and tolerability from all subjects who receive at least one dose of study drug will be evaluated for safety and tolerability. Data will be tabulated to examine the frequency.

Study Sites

1. Hackensack University Medical Center - John Theurer Cancer Center - Hackensack, NJ
2. Georgetown-Lombardi Cancer Center - Washington, DC

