4. OVERALL STUDY DESIGN

4.1. Study Design

This is a multicenter, open label study of Dara+Pom+Dex combined with ATRA in patients progressing on a Dara+Len+Dex regimen. The study is expected to enroll up-to a maximum of 42 patients (20-32 subjects previously exposed to Dara + Len + Dex; 10-22 subjects previously exposed to Dara + Pom + Dex)..

The phase 1b portion will follow a standard 3+3 dose escalation design with two dose levels and up to 12 patients. Under this design, the investigators will evaluate dose levels as follows:

- Dose level 1 - ATRA 35.5 mg/m²/day on days -2,-1 and 1 on a 28-day cycle in combination with daratumumab, pomalidomide, and dexamethasone
- Dose level 2 – ATRA 45 mg/m²/day on days -2,-1 and 1 on a 28-day cycle in combination with daratumumab, pomalidomide, and dexamethasone

During the dose-escalation phase and after the first cycle, and after the first cycle, patients who have not experienced a DLT, have not shown signs of PD, and in the opinion of the investigator would continue to benefit from treatment may receive additional cycles of treatment.

The phase 2 portion will be conducted in two stages. In the first stage, 10 patients will be accrued. A safety and efficacy analysis will be conducted 3 months after accrual of the first 10 patients. If there are 2 or fewer responses in these 10 patients, the study will be stopped due to futility. If the stopping rules for safety are met, then the study will be stopped due to toxicities. Otherwise, accrual will continue for a maximum of 42 in phase 1b and phase II combined.

During 28-day treatment cycles, patients will receive Dara 1800 mg subcutaneous (SC) at their current dose upon enrollment onto the study depending on their cycle. (If they are on cycles 1-2 then they will receive Dara 1800 mg SC days 1,8,15,22; if they are on cycles 3-6 they will receive Dara 1800 mg SC days 1 and 15; if they are on cycle 7 or beyond they will receive Dara 1800 mg SC on day 1).

Pomalidomide will be administered at the patient's currently tolerated dose (4,3, or 2 mg po daily) on days 1-21. For patients progressing on daratumumab, lenalidomide, and dexamethasone, the starting dose of pomalidomide will be 4 mg per standard of care.

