9.2. Sample Size and Power Considerations

Phase 1b of the study will follow a standard 3 + 3 dose escalation design as described in Section 7.4. With two dose levels, the study will need between 3 and 12 patients depending on toxicities. Patients will be considered evaluable in phase 1b for MTD assessment provided that they have not missed any of their doses of ATRA in Cycle 1, or have had a DLT. Patients who are not considered evaluable as defined above will be replaced.

For the phase 2 portion:

Approximately 20 patients who fulfill the eligibility criteria of the protocol will be enrolled. The phase 2 study will use a Simon 2-stage minimax design, whereby 10 patients will be accrued in the first stage, and ORR assessed, before moving to the next stage. If ≥ 3 objective responses are observed in the first stage, the study will proceed to the next stage; and an additional 10 patients will be accrued. If there are 8 or

more responses among the 20 patients, the combination will be declared worthy for further evaluation. The null hypothesis that the true response rate is 25% or less will be tested against a one-sided alternative of 48% or higher at the one-sided type I error of 0.10. This design yields a type I error rate of 0.096 and power of 0.806 when the true response rate is 48%. The probability of early stopping due to futility is approximately 52.0%.

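### The phase 2 ORR test is defined by two incompatible Simon minimax designs (30% vs 50% in 12/28 patients; 25% vs 48% in 10/20), and nothing says which governs

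*Combined protocol and SAP*

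**What the plan says.** **Protocol Summary, Statistical Considerations.** The Brief Statistical Rationale gives a Simon minimax design for phase 2: null 30%, alternative 50%, one-sided type I error 0.10, power 80%. The stage 1 rule is "If there are 4 or fewer responses in these 12 patients, the study will be stopped due to futility". Another 16 patients follow, and "The null hypothesis will be rejected if 12 or more responses are observed in 28 patients". The power paragraph then says "This Simon's two-stage design yields a type I error rate of 0.095 and power of 0.802 when the true response rate is 48" percent, and "The probability of early stopping due to futility is approximately 49.2" percent.

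**Section 9.2.** For the same phase 2 portion: "The null hypothesis that the true response rate is 25% or less will be tested against a one-sided alternative of 48% or higher", at one-sided type I error 0.10. Stage 1 has 10 patients, and the trial continues at 3 or more responses. Ten more are added, and with 8 or "more responses among the 20 patients, the combination will be declared worthy for further evaluation". The stated figures are type I error 0.096 and power 0.806 at 48%, and "The probability of early stopping due to futility is approximately 52.0" percent.

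**Other sections.** Section 4.1 carries the 10-patient futility rule ("If there are 2 or fewer responses in these 10 patients, the study will be stopped due to futility"), then lets accrual run to a cap of 42 over both phases, with no stage 2 size or success bound. Section 9.5 repeats the same futility rule. Section 9.4 times its two safety looks on 10 and then 10 more patients. Section 9.1 defers detailed methods to a statistical analysis plan. No text in the combined document ranks one design over the other.

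**The concern.** The null, the alternative, both stage sizes, the total and both boundaries differ for what is one primary test. Neither design is assigned to a particular prior-exposure cohort, so they cannot be read as two tests for two groups.

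The stop/go decision and the success claim for the primary endpoint therefore have no single rule:

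- 3 responders in the first 10 and still 3 after 12 means continue under Section 9.2 and stop under the Summary.
- 8 responders in the first 20 and 11 in 28 is a success under Section 9.2 and a failure under the Summary.

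The main open point is the null rate. Neither passage justifies its choice. The Pom + Dex response rates that Section 4.2 quotes from three trials including lenalidomide-refractory patients (25%-30%, 32%-38% and 33%-43%) do not single out either 25% or 30%.

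**Working it through.** **Inputs.** Summary: n1 = 12, stop at ≤ 4, n = 28, success at ≥ 12, null 0.30, alternative 0.50. Section 9.2: n1 = 10, stop at ≤ 2, n = 20, success at ≥ 8, null 0.25, alternative 0.48.

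**Formulas.** With futility bound r1 and success bound s:

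- P(success | p) = Σ over x from r1+1 to n1 of C(n1,x) p^x (1−p)^(n1−x) × P(Bin(n−n1, p) ≥ s−x)
- P(early stop | p) = P(Bin(n1, p) ≤ r1)

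**Step 1: each design against its own stated figures.**

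| Design | Type I error at own null | Power | Early stop at null |
|---|---|---|---|
| Section 9.2, stated | 0.096 | 0.806 at 48% | 52.0% |
| Section 9.2, computed | 0.0956 | 0.8059 at 48% | 52.6% |
| Summary, stated | 0.095 | 0.802 at 48% | 49.2% |
| Summary as printed (≤ 4 of 12), computed | 0.0782 | 0.6653 at 48%; 0.7297 at 50% | 72.4% |
| Summary with ≤ 3 of 12, computed | 0.0954 | 0.7404 at 48%; 0.8020 at 50% | 49.25% |

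Section 9.2 reproduces apart from a small difference in early stopping: 0.0563 + 0.1877 + 0.2816 = 0.5256.

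The Summary does not reproduce. At 30%, P(0 to 3 of 12) = 0.0138 + 0.0712 + 0.1678 + 0.2397 = 0.4925, which is the stated early-stopping figure. Including 4 adds 0.2311 and gives 0.7237 (unrounded terms). So the stated figures belong to a bound of 3 or fewer, with power taken at 50%.

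An exhaustive search at type I error 0.10 and power 0.80 gives 3/12 with success at 12/28 as the minimax design for 30% vs 50%, and 2/10 with success at 8/20 for 25% vs 48%. The Summary therefore holds a genuine second design with two misprints (4 for 3, and 48% for 50%), not a garbled copy of Section 9.2.

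**Step 2: error of the Section 9.2 rule at the Summary's null.** P(success | 0.30) with 2/10 and 8/20 is 0.2153, more than twice the 0.10 limit.

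**Step 3: how often the rules disagree.** Take one sequence of 28 patients and split it into patients 1-10, 11-12, 13-20 and 21-28, with independent binomial counts at a common rate. Enumerate all outcomes and apply both rules to each.

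| True ORR | Different final verdict, ≤ 4 of 12 | Different final verdict, ≤ 3 of 12 |
|---|---|---|
| 25% | 0.076 | 0.075 |
| 30% | 0.145 | 0.139 |
| 40% | 0.222 | 0.196 |
| 48% | 0.166 | 0.128 |

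Most of the printed-rule conflict is success under Section 9.2 alone: 0.141 of 0.145 at 30%, and 0.210 of 0.222 at 40%. Cross-check at 30%: success under either rule is 0.2195, so both succeed with 0.2153 + 0.0782 − 0.2195 = 0.0740, and Section 9.2 alone with 0.2153 − 0.0740 = 0.1413.

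At stage 1, Section 9.2 continues while the Summary stops with probability 0.341 at 30% and 0.271 at 40% as printed, or 0.131 and 0.077 with 3 of 12. The reverse conflict is 0 as printed, and 0.021 and 0.019 with 3 of 12.

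**Step 4: choosing the rule after the data.** Success under either printed rule has probability 0.097 at 25% and 0.220 at 30%, against 0.096 and 0.215 for Section 9.2 alone. The post hoc choice itself adds little; the unsettled null is what matters.

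**The case against.** The strongest reply is that the body of the protocol points one way. Sections 4.1, 9.2, 9.4 and 9.5 all work with 10 or 10 + 10 patients, Section 9.2 reproduces its type I error and power, and the outlier is a synopsis paragraph that fails its own arithmetic. The enrolment text leans the same way. The cohort ranges are 20-32 and 10-22, each its lower end plus 12; and 20 + 10 + 12 = 42 is exactly the cap, whereas 28 + 10 + 12 = 50 exceeds it.

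That is fair evidence of intent, but it does not settle the rule. A total of 28 lies within 20-32, and 12 + 28 = 40 fits under 42 if phase 1b supplies the Dara + Pom + Dex patients. Section 4.1 continues to the cap rather than to 20, and the Summary places its primary analysis after up to 42 patients in both phases.

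It can also be said that part of the stage 1 conflict comes from the misprinted 4. That stands: correcting it lowers the stage 1 conflict considerably. The final-verdict conflict falls only to 0.139 at 30% and 0.196 at 40%.

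Finally, the rates in Section 4.2 are for a doublet, not for the study regimen after daratumumab. They do not identify the right null; they show only that the protocol's own background does not choose between the two. The 52.0% against 52.6% difference in Section 9.2 is minor.

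**Conclusion.** The concern holds and should be resolved before the interim look. Two different designs stand in current text for the primary phase 2 test, with no statement of precedence. They give different final verdicts with probability 0.076 to 0.222 over true ORRs of 25%, 30%, 40% and 48% as printed, or 0.075 to 0.196 once the Summary's stage 1 bound is corrected. The Section 9.2 rule keeps its 0.10 limit only if 25% is the right null. Separately, the Summary's printed boundary does not deliver its stated type I error, power or early-stopping probability.

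These figures assume independent responses at one common rate and both rules applied to the same patients in the same order. They also assume that no separate analysis plan, outside the combined document, settles the choice.

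**What to change.** Choose and justify one null rate before the interim look, then state one design identically in the Protocol Summary and in Sections 4.1, 9.2, 9.4 and 9.5.

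- **If 25%/48% with 10/20 is kept:** replace the Summary's hypotheses, boundaries and operating characteristics with those of Section 9.2. The early-stopping figure can be corrected to 52.6% at the same time. The cost is wording only. Expected size at 25% is 10 + 10 × (1 − 0.5256) = 14.7.
- **If 30%/50% with 12/28 is kept:** correct the stage 1 bound to 3 or fewer of 12 and the power rate to 50%, and change Sections 4.1, 9.2, 9.4 and 9.5 to match. The cost is up to 28 − 20 = 8 more phase 2 patients than Section 9.2 plans. Expected size at 30% is 12 + 16 × (1 − 0.4925) = 20.1. Confirm that the 42-patient cap and the cohort ranges can supply 28 patients for the test.

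In either case, state whether phase 1b patients count towards the test and whether its denominator is the Dara + Len + Dex cohort named in the primary endpoint; the 8-patient cost falls on that cohort only if so. A cross-reference from Sections 4.1 and 9.5 to the final success rule would help but is secondary.

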1. INTRODUCTION

Multiple myeloma (MM) is a rare and incurable progressive neoplastic disease that accounts for 10% of all hematological malignancies. It was estimated that in 2017 30,280 new cases and 12,590 deaths from the disease occurred in the United States (Siegel, 2017; The Cancer Society, 2017). It was estimated in 2016 that 8,700 new cases and 4,200 deaths from the disease occurred in Japan (Cancer Statistics in Japan, 2016).

Multiple myeloma (MM) is typically sensitive to a variety of cytotoxic drugs. Although responses are typically durable, relapse is an expected part of the disease course and MM is not considered curable with current approaches. Treatment of MM has been rapidly evolving with the introduction of new classes and new generation of drugs: immunomodulating drugs (IMiDs), proteasome inhibitors (PIs), monoclonal antibodies, and histone deacetylase (HDAC) inhibitors.

In addition, there is increasing understanding of the tumor biology, creating the rationale of new combination therapies (Anderson, 2011; Hideshima, 2002; NCCN, 2018). In recent years, innovative therapies such as proteasome inhibitors and immunomodulators have improved the prognosis for previously treated MM subjects (Kumar, 2008). However, the disease follows a relapsing course in the majority of patients, regardless of treatment regimen or initial response to treatment. Multiple myeloma remains incurable using conventional treatments, with a median survival duration of approximately 5 years (Richardson, 2007a). Therefore, there is a need for more effective therapeutic options for the treatment of relapsed or refractory multiple myeloma.

Despite new advances in treatment, the disease is still characterized by a relapsing course and is invariably fatal. Nearly all patients with MM relapse eventually become refractory to treatment. This population is particularly challenging to treat and with low survival rates due to a number of patient- and disease-related factors, including patient comorbidities, biological heterogeneity, and toxicities from prior treatments. For example, patients with MM whose disease develops resistance to bortezomib and Lenalidomide have a median OS of 9 months (Kumar et al, 2012).

Daratumumab (Dara) is a human IgG1-k monoclonal antibody to CD-38 that effectively mediates destruction of CD-38 expressing malignant plasma cells. It was approved by the Food and Drug Administration (FDA) in the United States in November 2015 as a single agent for the treatment of patients with MM who have received at least three prior therapies. CD38 serves not only as an antigen but also as an enzyme that catalyzes the metabolism of cyclic adenosine diphosphate ribose and nicotinic acid adenine dinucleotide phosphate (Lee, 2006). Thus, representing an important immunotherapy target due to its high expression on malignant plasma cells and low expression on other normal lymphoid and myeloid cells as well as being an important modulator of intracellular signaling (Chillemi et al, 2013).

Daratumumab has been shown to have efficacy in combination with immunomodulatory (IMiD) agents such as Lenalidomide (Len) and Pomalidomide (Pom). The POLLUX trial was a randomized trial which examined the combination of Dara with Len and Dexamethasone (Dex) compared to Len-Dex alone in patients relapsed or refractory multiple myeloma who had ≥ 1 prior therapy. With a median follow-up of 13.5 months, median progression free survival (PFS) had not yet been reached in the triplet combination

compared to 18.4 months with Len-Dex alone (HR 0.37; 95% CI: 0.27, 0.52; $p<0.0001$)(Dimopoulos et al, 2016). Overall response rate (ORR) with Dara-Len-Dex was 91.3%. A phase 2 single arm trial evaluated Dara with Pom and Dex in patients who had received ≥ 2 prior therapies. Overall response rate was 60% with 13.6% achieving a complete response (CR) or better (Chari et al, 2017).

Daratumumab has been evaluated with Pomalidomide and Dexamethasone (Pom-Dex) in patients with relapsed/refractory multiple myeloma with ≥ 2 prior lines of therapy and who were refractory to their last line of treatment (Chari A, Suvannasankha A, Fay JW, Arnulf B, et al. Blood, 2017). The safety profile of Daratumumab plus Pom-Dex was similar to that of Pom-Dex alone, with the exception of Daratumumab-specific infusion-related reactions (50%) and a higher incidence of neutropenia although without an increase in infection rate. ORR was 60% and was generally consistent across all subgroups, with an ORR of 58% in double refractory patients. At a median follow-up of 13.1 months, the median PFS was 8.8 months and median OS was 17.5 months. The estimated 12-month survival rate was 66% (Ajai et al, 2017).

Factors that determine susceptibility of MM cells to Daratumumab include levels of target antigen CD38 and expression levels of the complement inhibitory proteins CD55 and CD59. Experiments with isogenic MM cell lines expressing different levels of CD38 revealed that the level of CD38 expression is an important determinant of Dara-mediated ADCC and CDC (Nijhof et al, 2015). At time of progression, there is a reduced level of CD38 on MM cells, whereas CD55 and CD59 are increased. In a cohort of 102 patients treated with Daratumumab monotherapy, pretreatment levels of CD38 expression on MM cells were significantly higher in patients who achieved at least a partial response (PR) compared with patients who achieved less than PR. CD38 expression was reduced in both bone marrow-localized and circulating MM cells, following the first Daratumumab infusion. CD38 expression levels on MM cells were again increased following Daratumumab discontinuation. In contrast CD55 and CD59 levels were significantly increased on MM cells at the time of progression (Nijhof et al, 2016). These preclinical and clinical data indicate that the downregulation of CD38 and the upregulation of CD55 and CD59 are involved in the development of Dara-resistant multiple myeloma.

All-trans retinoic acid (ATRA) has been shown in both cell lines and primary MM samples to increase CD38 expression levels and to reduce expression of the complement-inhibitory proteins CD55 and CD59(Nijhof et al, 2015). This resulted in significant enhancement of activity of Daratumumab in vitro and in humanized MM mouse models. Daratumumab and ATRA exhibit a strong synergy in MM cells derived from Dara-naïve patients and from patients with Dara-refractory disease, providing preclinical rationale for further evaluation of Daratumumab combined with ATRA in MM patients. Preliminary data from phase 1 trials combining Daratumumab and ATRA have shown that the combination is safe using ATRA 45 mg/m²/day dose.

It is our hypothesis that therapy with the addition of ATRA to the combination of Dara and Pomalidomide (Pom) with Dexamethasone (Dex) in patients progressing on Dara plus an IMiD + Dex will result in a significant clinical response. The aim of this study is to determine the ORR of Dara + Pom + Dex + ATRA in patients progressing on Daratumumab + Lenalidomide + Dex and to determine whether this combination is suitable for clinical use and evaluation in subsequent randomized trials. To this end, the ORR of Dara +

Pom + Dex in combination with ATRA will be determined for patients relapsing on Dara + Len + Dex or Dara + Pom + Dex.

